## **Outcomes**

Outcomes related to feasibility were percentage of eligible subjects that accepted participation (recruitment), percentage of included subjects that finished the 12 months intervention period (retention), the feasibility of undertaking functional assessment and use of ONS/snacks assessed by 24 hour recalls (compliance).

The primary outcome was efficacy of the interventions assessed as weight change from baseline to one year from admission to the hospital. Assessment of body composition i.e.

fat mass, fat free mass and muscle mass was conducted using a portable, multi- frequency (20kHz, 100kHz) bioelectrical impedance analysis (BIA) device (InBody230 Co., Ltd. Korea). The method has previously been validated in stable COPD patients. (Schols, Broekhuizen, Weling-Scheepers, & Wouters, 2005)

The secondary outcome measures were QoL measured using the St George's Respiratory Questionnaire (SGRQ). This validated questionnaire is based on 76 items used to calculate three component scores: symptoms, activity and impact, and a total score. A score of 100 represents worst possible health status and a score of 0 represents best possible health status. (Jones, Quirk, Baveystock, & Littlejohns, 1992) A change of 4 points in the SGRQ total score is considered the minimum clinically relevant difference. (Jones, 2002)

Other outcomes measures included were forced expiratory volume in one second (FEV1), forced vital capacity (FVC) measured by spirometry (Jaeger MS-PFT®, Care Fusion, San Diego, USA), (Vogelmeier et al., 2017) functional performance using several tests validated in COPD patients were included: six-minute walk distance (6MWD), (Singh et al., 2014) timed up and go (TUG), (Mesquita et al., 2016) 30 second chair stand (Kato et al., 2014) and hand-grip strength (HGS) (Puhan, Siebeling, Zoller, Muggensturm, & ter Riet, 2013) measured by a handheld dynamometer (Jamar® Sammons Preston Rolyan, Boilingbrook, IL, USA) and energy- and protein intake during hospital stay and at home (two and four weeks after discharge).

Total energy- and protein intake during hospital stay was estimated using a validated plate diagram sheet (Bjornsdottir et al., 2013; Vilhjalmsdottir, Hinrikssdottir, Pordardottir, Porsdottir, & Gunnarsdottir, 2013) for three days, starting on the first day of participation in the study and after the intervention had started.

Energy- and protein intake at home was assessed using the 24-hour recall method, (Salvador Castell, Serra-Majem, & Ribas-Barba, 2015) two and four weeks after hospital discharge and analysed using the ICEFOOD nutritional analysis program. (Thorgeirsdottir et al., 2011) For full details of study assessments (see Appendix 1).

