**ID: COPD-141316051**

**NCT02251496**

## **COPD: Oral Nutrition Supplements vs. Energy- and Protein Dense in Between Meal Snacks.**

**[name]**

**12/23/2020**

## METHODS

### Study design and participants

This study was a randomised trial and registered at clinicaltrials.gov on September 25, 2014. ClinicalTrials.gov identifier: [NCT02251496](https://clinicaltrials.gov/ct2/show/NCT02251496). The study was approved by the National Bioethics Committee (VSN14-066-S1), Chief medical officer Landspitali (LSH 68-14) and Data Protection Authority (2014/908) and conducted in line with the Declaration of Helsinki. The study follows the CONSORT 2010 statement: extension to randomised pilot and feasibility trials. (Eldridge et al., 2016)

Patients with a clinical diagnoses of COPD who had been recently admitted to the Department of Respiratory Medicine at Landspitali University Hospital were screened for possible nutritional risk (score  $\geq 4$ ) by a trained researcher using a validated nutritional screening tool. (Ingadottir et al.; Thorsdottir, Gunnarsdottir, & Eriksen, 2001) The Icelandic Simple Screening (ISS) used is recommended by the clinical guidelines for hospital nutrition at Landspitali (Friðriksdóttir, 2011) and has been validated against a full nutritional assessment in COPD patients (Thorsdottir et al., 2001) and predicts mortality in COPD patients. (Ingadottir et al.) ISS gathers information on BMI, unintentional weight loss, age, co-morbidities, recent hospitalisation and a range of symptoms that impact nutritional intake during the last weeks or months (vomiting, diarrhoea, loss of appetite or nausea, difficulties in chewing or swallowing).

All eligible patients who were able to eat orally, and had an anticipated length of hospitalisation of  $>3$  days were invited to participate in the study. The most common reason for admission was acute exacerbation of COPD. Written informed consent was obtained from all participants.

Patients diagnosed with cancer, dysphagia, food allergy or intolerance and anatomical obstructions preventing oral food intake were excluded. Patients not able to sign informed consent due to cognitive issues were also excluded.

Socio-demographic data (age, gender and smoking status) were collected from electronic medical records SAGA (TM software 3.1.39.9).

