### **Statistical analysis**

All statistical analyses were undertaken using IBM SPSS Statistics 24 and the level of significance was set at 0.05.

Our original power calculations were based on the primary outcome of difference in weight gain between the groups and change in weight to one year. Due to low recruitment rate

and lower participation rates than expected, post-hoc power calculations were performed based on our results.

The Kolmogorov-Smirnov test was used to test data normality. The independent t-test was used to test for differences between continuous data at baseline and the Pearson's chi-squared test was used for categorical data. Intention-to-treat analyses were conducted where the last observations were carried forward and used to assess treatment efficacy. All patients with at least two measures (baseline and one other) were included. Repeated measures ANCOVA was conducted to analyse mean changes in each follow up.

Collins, P. F., Stratton, R. J., & Elia, M. (2012). Nutritional support in chronic obstructive pulmonary disease: a systematic review and meta-analysis. *Am J Clin Nutr*, 95(6), 1385-1395. doi:10.3945/ajcn.111.023499

Eldridge, S. M., Chan, C. L., Campbell, M. J., Bond, C. M., Hopewell, S., Thabane, L., . . . group, P. c. (2016). CONSORT 2010 statement: extension to randomised pilot and feasibility trials. *Pilot Feasibility Stud*, 2, 64. doi:10.1186/s40814-016-0105-8

Ferreira, I. M., Brooks, D., White, J., & Goldstein, R. (2012). Nutritional supplementation for stable chronic obstructive pulmonary disease. *Cochrane Database Syst Rev*, 12, CD000998. doi:10.1002/14651858.CD000998.pub3

Friðriksdóttir, A. J., & Möller, P. H. . (2011). Clinical guidelines on patients nutrition. Retrieved from <http://www.landspitali.is/lisalib/getfile.aspx?itemid=28242>

Ingadottir, A. R., Beck, A. M., Baldwin, C., Weekes, C. E., Geirsdottir, O. G., Ramel, A., . . . Gunnarsdottir, I. Two components of the new ESPEN diagnostic criteria for malnutrition are independent predictors of lung function in hospitalized patients with chronic obstructive pulmonary disease (COPD). *Clinical Nutrition*. doi:<https://doi.org/10.1016/j.clnu.2017.05.031>

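### The supplied text gives no score for being unable to do the walk, chair-stand or timed-up-and-go test, and the stated missing-data rules could leave lost function uncounted

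*Protocol*

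**What the plan says.** The protocol's Outcomes section names weight change as primary and the SGRQ as secondary. The functional tests come after these, among the other outcomes: "functional performance using several tests validated in COPD patients were included: six-minute walk distance (6MWD". The list there also has timed up and go and the 30-second chair stand. The same section counts "the feasibility of undertaking functional assessment" among the feasibility outcomes, without defining it or saying whether it is compared by arm. Details are referred elsewhere: "For full details of study assessments (see Appendix 1". That appendix is not in the supplied text.

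The protocol's Statistical analysis section has one general set of data-handling rules, which the SAP repeats word for word:
- On gaps in the data, the rule is: "Intention-to-treat analyses were conducted where the last observations were carried forward and used to assess treatment efficacy".
- On who enters the analysis, the rule is: "All patients with at least two measures (baseline and one other) were included".
- On the model, the text reads: "Repeated measures ANCOVA was conducted to analyse mean changes in each follow up".

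Neither document makes an exception for a patient who attends but cannot perform a test.

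On the population, Study design and participants says: "The most common reason for admission was acute exacerbation of COPD".

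**The concern.** These are recently admitted inpatients, mostly with an exacerbation, followed for a year. Some will plausibly be unable to walk for six minutes or rise from a chair at baseline, and others will lose that ability later. By making testability an outcome, the plan itself allows for this.

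Inability for health reasons differs from a missed visit. The patient is present and the result is known: it is the worst on the scale. In the chair stand it is 0 stands. In timed up and go there is no natural worst time, but the patient plainly ranks behind the slowest person who finished. A general missing-data rule treats this known bad result as an unknown one.

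At stake is what the functional results describe. They could cover only patients fit enough to be tested, with the largest changes (able to unable, unable to able) left out.

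**Working it through.** The documents give no figure on this point, so there is nothing to reproduce. The check has two parts.

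**1. Applying the stated rules.** Assume that inability is left without a value and that the two-measure rule applies separately to each test.

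- (a) Unable at baseline: there is no baseline measure, so the patient is excluded for that test, even if able later. A recovery is lost.
- (b) Able at baseline and at one or more follow-ups, then unable: the last result is carried forward. The loss is not counted.
- (c) Able at baseline, unable at every follow-up: there is no second measure, so the patient is excluded. The loss is not counted.

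The second assumption matters less than the first. If the two-measure rule applied per patient across all outcomes, group (a) would still have no baseline from which to compute a change. Group (c) could then have its baseline carried forward, giving a change of zero. The loss is uncounted either way.

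**2. Illustration of size.** Every input here is an assumption, because the documents give no inability rates and no test values.

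- Last good walk distance L: 200 to 300 m, equal to baseline.
- Patients still able: no true change.
- Share u who become unable: varied by arm.
- Inability is set to 0 m only to express the effect in metres.

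Under carry-forward or exclusion, the mean change is 0 in each arm. With inability as 0 m, the mean change in an arm is −u × L, and the between-arm difference is (u2 − u1) × L.

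| Unable, arm 1 v arm 2 | Difference, stated rules | Arm changes, inability as 0 m | Difference, inability as 0 m |
|---|---|---|---|
| 10% v 10% | 0 m | −20 to −30 m in each | 0 m |
| 10% v 20% | 0 m | −20 to −30 m v −40 to −60 m | 20 to 30 m |
| 10% v 30% | 0 m | −20 to −30 m v −60 to −90 m | 40 to 60 m |
| 20% v 40% | 0 m | −40 to −60 m v −80 to −120 m | 40 to 60 m |

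The first row shows that equal inability produces no between-arm error, yet a fall of 20 to 30 m disappears from each arm.

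For group (a), the protocol's Procedures section gives 76 eligible patients; the number randomised is not stated. If a share b could not do a test at baseline, an analysis that requires a baseline keeps at most 76 × (1 − b): 68.4 at b = 10%, 60.8 at 20% and 53.2 at 30%, or about 68 down to 53 patients.

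**The case against.** The strongest reply is that nothing in the documents says inability is recorded as missing. Appendix 1 may contain a scoring rule. Walk distance and stand count have a natural zero, which may already have been used. This stands, and it is why the point is conditional. A reader might infer that the plan itself drops the sickest patients and hides decline. The supplied text does not support that: it is silent on scoring, and it does not say that the two-measure rule applies per test.

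A reader might also infer that everyone who becomes unable is given their last good result. That is wrong for group (c), who are excluded when the rule applies per test.

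Next, a between-arm error needs unequal inability. The documents give no rates, and the products are closely matched (means of 280 kcal and 11 g protein against 286 kcal and 11 g). This stands too. The within-arm effect does not depend on it.

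It can also be said that the feasibility outcome already deals with untestable patients. It may lead to their being reported, but it has no definition, and reporting them does not change the values that enter the ANCOVA.

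Lastly, treating inability as the worst result is a choice of estimand. Making it the main analysis would be open to debate, so it is proposed below as an addition for the walk and timed up and go.

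**Conclusion.** The concern holds in conditional form. The supplied text states no scoring rule for inability. If inability has no value and the two-measure rule applies per test, the stated rules exclude groups (a) and (c) and carry forward a better result for group (b). Loss of function within each arm is then understated, recoveries among those unable at baseline are left out, and a between-arm difference is masked if inability differs by arm. Its direction and size are unknown.

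The metre figures are purely illustrative. It would be tempting to quote a multiple, but any such ratio is fixed by the assumptions. Suppose a baseline of 8 stands carried forward, a gain of 1 in able patients, and 25% v 10% unable. The difference is then 0.15 × (9 − 8) = 0.15 stands under carry-forward and 0.15 × 9 = 1.35 with inability as 0. The ratio is 9/(9 − 8) = 9 at any unequal pair of inability rates, so it says nothing about this trial. Nor would arms that differ in decline necessarily look alike: decline among patients still able to do the test is measured.

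Severity is low. These outcomes are neither primary nor secondary, the trial was converted to a feasibility design, and the weight result is unaffected.

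**What to change.** - State the rule for each test. Do not carry a result forward when the patient was seen but unable for health reasons. Count this as 0 in the 30-second chair stand.
- For the walk and timed up and go, add a sensitivity analysis beside the planned ANCOVA. Rank inability for health reasons worse than every measured value (behind the shortest distance and the slowest time), and compare arms on ranks.
- Report the functional feasibility outcome as the percentage able per test, arm and visit, with all randomised patients alive at that visit as denominator.
- The documents are written after the fact and do not say that reasons for an absent test were noted. Where a reason was not recorded, say so, and show results with those patients treated both as unable and as missing.
- If Appendix 1 already contains a scoring rule, bring it into the SAP and say how it fits with carry-forward.

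The cost is some outcome coding and a little more analysis. Ranks are less direct to read than metres or seconds, which is a reason to keep the planned ANCOVA alongside.

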### **Statistical analysis**

All statistical analyses were undertaken using IBM SPSS Statistics 24 and the level of significance was set at 0.05.

Our original power calculations were based on the primary outcome of difference in weight gain between the groups and change in weight to one year. Due to low recruitment rate

and lower participation rates than expected, post-hoc power calculations were performed based on our results.

The Kolmogorov-Smirnov test was used to test data normality. The independent t-test was used to test for differences between continuous data at baseline and the Pearson's chi-squared test was used for categorical data. Intention-to-treat analyses were conducted where the last observations were carried forward and used to assess treatment efficacy. All patients with at least two measures (baseline and one other) were included. Repeated measures ANCOVA was conducted to analyse mean changes in each follow up.

Collins, P. F., Stratton, R. J., & Elia, M. (2012). Nutritional support in chronic obstructive pulmonary disease: a systematic review and meta-analysis. *Am J Clin Nutr*, 95(6), 1385-1395. doi:10.3945/ajcn.111.023499

Eldridge, S. M., Chan, C. L., Campbell, M. J., Bond, C. M., Hopewell, S., Thabane, L., . . . group, P. c. (2016). CONSORT 2010 statement: extension to randomised pilot and feasibility trials. *Pilot Feasibility Stud*, 2, 64. doi:10.1186/s40814-016-0105-8

Ferreira, I. M., Brooks, D., White, J., & Goldstein, R. (2012). Nutritional supplementation for stable chronic obstructive pulmonary disease. *Cochrane Database Syst Rev*, 12, CD000998. doi:10.1002/14651858.CD000998.pub3

Friðriksdóttir, A. J., & Möller, P. H. . (2011). Clinical guidelines on patients nutrition. Retrieved from <http://www.landspitali.is/lisalib/getfile.aspx?itemid=28242>

Ingadottir, A. R., Beck, A. M., Baldwin, C., Weekes, C. E., Geirsdottir, O. G., Ramel, A., . . . Gunnarsdottir, I. Two components of the new ESPEN diagnostic criteria for malnutrition are independent predictors of lung function in hospitalized patients with chronic obstructive pulmonary disease (COPD). *Clinical Nutrition*. doi:<https://doi.org/10.1016/j.clnu.2017.05.031>

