### **Procedures**

This study was originally designed as a randomized trial to investigate the effects of snacks on body weight and QoL in COPD patients compared to ONS with a planned enrolment of 200 subjects (ClinicalTrials.gov, number [NCT02251496](#)). Despite screening 492 subjects only 76 subjects were eligible indicating that recruitment is challenging in this population and clinical setting. Recruitment rates were lower than expected which led to a change in the study protocol to a randomised feasibility trial as funding was limited to three years. One reason for low recruitment rates might be over strict inclusion criteria. More details on study recruitment are provided in the results.

Nutritional screening was undertaken on admission using the validated screening tool as recommended for use at the Landspitali. (Friðriksdóttir, 2011; Ingadottir et al.; Thorsdottir et al., 2001) A total score of  $\geq 4$  is considered ‘at nutritional risk’.

After providing informed consent, subjects were randomly allocated to one of two groups. Subjects in group 1 were provided with ONS and subjects in group 2 were provided with snacks (Table 1). The intervention started in hospital and was continued for 12 months after discharge from the hospital.

**Table 1** Nutritional content of each intervention products.

Oral nutritional supplement drinks			
Product	Portion size	Energy (kcal)	Protein (g)
Nutridrink compact (Nutricia) e.g. vanilla, banana, strawberry and chocolate	125 ml	300	12
Nutridrink compact fiber (Nutricia) -vanilla, strawberry and mokka	125 ml	300	12
Nutridrink (Nutricia) -vanilla, strawberry, banana, and chocolate	200 ml	300	12
Nutridrink juice style (Nutricia) e.g. blackcurrant, apple and orange	200 ml	300	8
Nutridrink creme (Nutricia) -forest fruit and chocolate	125 g	200	12
Mean		280	11
In-between meals snack			
Product	Portion size	Energy (kcal)	Protein (g)
Blueberry skyr with cream (MS Dairies)	Skyr 140 g Cream 20 ml	254	17
Two mini skyr with cream (MS Dairies) -vanilla, strawberry and banana	Skyr 167 g Cream 20 ml	274	16
Rye bread (Myllan) with liver paté (Ora) and butter (MS Dairies)	Rye bread 55 g Liver paté 40 g Butter 10 g	313	7
Pan bread (Myllan) with ham- and egg salat (Sómi)	Pan bread 47 g Salat 55 g	262	8
Oat biscuits (Frón) with butter, cheese and glass of milk (MS Dairies)	Oat biscuit 20 g Butter 10 g Cheese 20 g Milk 150 ml	342	12

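### Weight stays the primary efficacy outcome after the change to a feasibility trial, but the plan answers the lost precision only with post-hoc power and specifies no confidence interval or reference weight difference

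*Protocol*

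**What the plan says.** **The shortfall.** The protocol's Procedures section describes a trial "with a planned enrolment of 200 subjects" and then reports: "Despite screening 492 subjects only 76 subjects were eligible". It says that low recruitment and three-year funding led to a change to a randomised feasibility trial. Study design and participants names the CONSORT extension for pilot and feasibility trials.

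**The primary outcome.** The protocol's Outcomes section lists recruitment, retention, feasibility of functional testing and compliance as feasibility outcomes. It then states: "The primary outcome was efficacy of the interventions assessed as weight change from baseline to one year from admission to the hospital". For the secondary outcome it supplies a threshold: "A change of 4 points in the SGRQ total score is considered the minimum clinically relevant difference". It gives none for weight.

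**The analysis.** Statistical analysis, worded the same in the protocol and the SAP, sets significance at 0.05. It says the original power calculations concerned "difference in weight gain between the groups and change in weight to one year", without an effect size, SD, power or dropout rate. Because of low recruitment and "lower participation rates than expected", it says, "post-hoc power calculations were performed based on our results". On efficacy it says: "Intention-to-treat analyses were conducted where the last observations were carried forward and used to assess treatment efficacy". The model is a repeated measures ANCOVA. No confidence interval is mentioned in either document.

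**The concern.** When a trial ends well below its planned size, the useful question is which treatment differences the data still leave open. An interval read against a reference difference answers it. Post-hoc power does not, whichever inputs were used:

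- If it used the observed difference, it is a function of the p-value alone and adds nothing.
- If it used only the observed SD or the achieved number, it must have been set against some difference, and that difference is not stated.

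At stake is the reading of the primary outcome. Under the specified analysis, a non-significant weight result could mean that the two interventions differ by little, or that the trial was too small to tell. The plan specifies nothing that would separate the two.

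**Working it through.** **Inputs from the documents.** Planned size 200; 76 eligible of 492 screened; 1:1 allocation; significance level 0.05. The numbers randomised and analysed are not given, so 76 is an upper bound.

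**Assumptions.** A two-sided test; original power of 80% or 90%; loss of 0% to 30%. SD means the SD of the analysed weight change (residual SD if baseline-adjusted). The documents give no SD, so nothing is converted to kg.

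**1. The plan's own figure.** The 200 cannot be reproduced, because none of its inputs is given. Solved backwards with a two-sample t-test and no loss, 200 corresponds to a standardised difference of 0.398 at 80% power or 0.461 at 90%. This neither confirms nor refutes the 200.

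**2. Post-hoc power if the observed effect was used.** With z the normal deviate for the two-sided p-value, power = P(Z > 1.96 − z) + P(Z < −1.96 − z).

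| p-value | z | Post-hoc power |
|---|---|---|
| 0.05 | 1.960 | 50% |
| 0.10 | 1.645 | 38% |
| 0.30 | 1.036 | 18% |
| 0.50 | 0.674 | 10% |

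Sample size does not enter. A t-based version at 76 gives the same values to within half a percentage point.

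**3. Precision, whatever the post-hoc calculation used.** Half-width of the 95% interval for the group difference = t(0.975, n − 2) × √(4/n) SD.

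- n = 200: 1.972 × 0.1414 = 0.279 SD
- n = 76: 1.993 × 0.2294 = 0.457 SD, which is 0.457/0.279 = 1.64 times as wide

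The difference detectable with 80% power rises from 0.398 SD to 0.651 SD. Fewer than 76 analysed makes both figures worse.

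**4. Power left for the effect originally planned for, all 76 enrolled.** The planned difference is solved at 200 × (1 − planned loss). Power is then computed at 76 × (1 − actual loss).

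| Planned loss | Actual loss | Analysed, planned / actual | Power if sized for 80% | Power if sized for 90% |
|---|---|---|---|---|
| 0% | 0% | 200 / 76 | 40% | 51% |
| 20% | 20% | 160 / 60.8 | 40% | 51% |
| 30% | 30% | 140 / 53.2 | 40% | 51% |
| 0% | 30% | 200 / 53.2 | 30% | 38% |
| 30% | 0% | 140 / 76 | 54% | 66% |

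The first three rows agree only because the same loss is applied to both sizes. The plan reports participation below expectation, so equal loss cannot be taken for granted. The last row is nominal if all 76 are kept only by carrying observations forward.

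**The case against.** **The protocol reads as the Methods of a completed study.** It is in the past tense and refers to a results section that is not available, as is Appendix 1. The power inputs, an interval and the counts of observed weights could all appear there. This stands, and it limits the point to what the two documents specify. A reader might infer that no interval was ever reported; the documents do not support that.

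**No misuse is shown.** A reader might infer that the sponsor claims the two interventions work equally well, or used post-hoc power to explain away a non-significant result. Neither document says so, and neither shows a result. A reader might also take it as settled that the observed effect was used. The wording suggests this but does not establish it, so the p-value table applies only on that reading. The calculation could also have served to size a later trial. In that case the text would contain no statistical response at all to the precision of this trial's own weight result.

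**It is only a feasibility trial, and this is disclosed.** The disclosure deserves credit. It does not remove the point, because Outcomes still names efficacy on weight as primary and Statistical analysis still assesses efficacy at the 0.05 level.

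**The natural reference is the original planning difference, not a new one.** This stands. A calculation based on the difference in weight gain needs an assumed difference and SD, normally chosen before the data. A planning difference need not be a clinically meaningful one, but it comes first.

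**Carrying observations forward is a separate matter.** It is a missing-data choice and not a response to lost precision. It enters here only as a caution on any interval that is reported.

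**Conclusion.** The point holds as a gap in the specified analysis. No stated figure is shown to be wrong. The plan keeps an efficacy outcome as primary after losing at least 62% of its planned size ((200 − 76)/200). The only tool it specifies for that loss cannot show which weight differences remain open.

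The firmest figure is the half-width of at least 0.46 SD, against 0.28 SD at 200. It needs only the two-sided 5% level, equal arms and the upper bound of 76. The power figures rest on more: an assumed original power of 80% (90%), all 76 enrolled, and assumed losses. They are about 40% (51%) with equal loss, and about 30% to 54% (38% to 66%) when planned and actual loss are each 0% or 30%. A reader might take 40% as the trial's actual power; the documents do not allow a single figure.

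This should be fixed, because it governs how the primary outcome is read and the remedy is cheap.

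**What to change.** In the Statistical analysis section of both documents:

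1. Make the between-group difference in 12-month weight change, with its 95% confidence interval, the basis for interpretation in place of post-hoc power. Say that a non-significant result is not evidence of equal effect.
2. Disclose the difference, SD, power and dropout assumed in the original power calculation, and read the interval first against that difference and SD. Any meaningful difference added now needs a source outside this trial's results and a statement that it was chosen after the data existed.
3. Keep the post-hoc power calculation only as a record, stating the effect, SD and number it used.
4. Report how many 12-month weights were observed and how many were carried forward.

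The cost is some text, one interval and one count from existing data, plus retrieval of the original planning inputs; no new data are needed. There are two downsides. The weight result will be stated less strongly, and an interval from carried-forward data may be biased or too narrow, which should be said beside it.
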